2 SYNOPSIS OF STUDY

Phase 1, Double-Blind, Placebo-Controlled			
Assessment of Potential Interactions			
Between Intravenous Cocaine and			
Clavulanic Acid			
CLAV and Cocaine Interaction Safety Study			
Phase Ib			
This is a prospective, placebo controlled			
inpatient crossover safety study of 3 doses (250			
mg/day, 500 mg/day, 750 mg/day) of CLAV			
with an intravenous infusion of cocaine 40 mg.			
Subjects will be non-treatment seeking			
experienced cocaine dependent adults, ages 18-			
65 (N=12 completers, 21 estimated to enroll).			
Subjects will undergo a washout of the study			
drug for 5 half-lives between study drug			
administration sessions.			
Approximately 1.5 years.			
Temple Episcopal Hospital. Centennial 6 th			
floor, an inpatient medical unit with telemetry.			
To determine whether there are clinically			
significant adverse interactions between CLAV			
(250 mg/day; 500 mg/day; 750 mg/day) and			
intravenously administered cocaine in healthy,			
non-treatment seeking adults with cocaine use			
disorder.			
1. To evaluate whether administration of			
CLAV alters the pharmacokinetics (PK) of			
cocaine or its major metabolite,			
benzoylecgonine (BE).			
2. To determine PK of CLAV during treatment			
at 250 mg/day (low dose) and 500 mg/day			
(medium dose).			
3. To evaluate whether there are significant			
interactions between CLAV treatment			
concurrent with i.v. cocaine infusions of 40 mg			
by measuring the diameter of the pupil using a			
pupillometer.			
3. To evaluate whether CLAV treatment alters			
the subjective effects of cocaine, the perceived			
value of the dose of cocaine, and craving.			
4. To assess the effects of clavulanic acid on			
mood and personality and on the abuse			

	liability.		
Outcome Measures	Primary outcome measure is safety which will		
	be measured by AEs, BP, HR, and ECG QTc		
	interval. Secondary outcome measures include		
	PK parameters of cocaine, PK parameters of		
	CLAV, pupillometry. Exploratory outcome		
	measures are subjective effects measurements		
	assessed for cocaine in combination with		
	CLAV and CLAV alone. Effect on mood		
	(POMS), abuse liability (ARCI), and subjective		
	effects measurements (VAQ, VAS) will be		
	obtained. The effect of CLAV on cocaine		
	craving will be assessed using the CCQ-Brief.		
	The DVQ will be used to determine the		
	perceived value of each dose of cocaine.		
Number of Participants	12 completers, 21 estimated to enroll.		

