5.2.1.2 Primary, Secondary, and Exploratory Analyses

5.2.1.2.1 Primary Analyses: Safety is a primary assessment variable. The number of patients reporting each AE by treatment group and severity will be presented. Adverse events will be tabulated by body system and organ class. In addition, all adverse events (AE's) noted during the study will be listed. The listings will include each occurrence of the AE, when it was reported, the severity and the duration. Adverse event data will be compiled for CLAV at all doses (250 mg, 500 mg, 750 mg) and placebo and presented as summary statistics by organ system. Our primary analyses will compare the rates of occurrence of adverse events across the three-periods within each person. The data are gathered using a 3-period 3-treatment crossover design. Safety concerns constrain us to restrict the order of administration of the 2 study drug doses of CLAV, so each subject receives the doses in increasing order. Thus, we have three sequences: {PBO, Low (250 mg), Medium (500 mg)}, {Low, PBO, Medium}, and {Low, Medium, PBO}. One third of the subjects are randomized to each of these sequences. Each period is a 1 day session and the periods correspond to days 2, 3, and 4, providing 24 half-lives between administrations. The main explanatory variables in the models are: 1) a 3 level within-

subject factor representing drug condition (PBO, study drug low dose (SDlow), study drug medium dose (SDmedium), and 2) a three level factor representing period (1, 2, and 3). We use standard mixed effects (repeated measures) ANOVA models for binary responses in three-period three-treatment crossover designs to test our hypotheses.⁷³ An overall F-test of the condition effect will test for differences in response across the three drug doses, and contrasts will determine the pattern of differences (if any). Mixed effects models can allow for different error variances for different sessions, and other complex error structures as needed. As this study has only three repeated measures, a relatively simple covariance structure model (e.g. heterogeneous compound symmetry model) should be sufficient to account for within-subject correlations.

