Pharmacodynamic parameters (systolic and diastolic blood pressure, heart rate and QT_C interval, expressed as AUC, 2-minute values and maximal values) will be similarly analyzed. The COC infusions occur on the day of each session, providing three repeated sets of measures of each COC related response (change in HR, change in SBP, change in DBP, change in QT_c interval,).

HR and BP (systolic BP (SBP) and diastolic BP (DBP)) and QT_C induced by cocaine infusion will be compared to HR and BP and QT_C measurements before the cocaine infusion to assess change. BP and HR and QT_C changes after infusion given after CLAV (250 mg, 500 mg, 750 mg) will be compared to those without CLAV. We will compare the distribution of Area Under Curve (AUC) summaries of the within-period repeated measures of changes in vital signs (heart rate, systolic blood pressure, diastolic blood pressure) across the three-periods within each person as described above.

 QT_C interval measured by the ECG induced by cocaine infusion will be compared to QT_C interval before the cocaine infusion to assess change. QT_C interval changes after infusion given after CLAV (250 mg, 500 mg, 750 mg) will be compared to those without CLAV. We will compare the distribution of Area Under Curve (AUC) summaries of the within-period repeated measures of changes in QTc interval across the three-periods within each person as described above.

5.2.1.2.2 Secondary Analyses: The pharmacokinetic parameters will be statistically analyzed using a repeated measure analysis of variance model.

5.2.1.2.3 Exploratory Analyses: Subjective effects of cocaine, as measured by check lists, visual analog and rating scales, will be listed for each patient and summarized for each group. Adverse events for the CLAV 750 mg group will be analyzed as described above for the lower CLAV doses. Adverse events for the subset of subjects stabilized on Buprenorphine will be analyzed as described above.

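### If the one covariance structure the SAP names is fitted to BP, HR and QTc in 12 completers and tested without a small-sample correction, the overall F-test rejects about 9–10% of the time at an assumed nominal 5%

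*Combined protocol and SAP*

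**What the plan says.** Section 5.2.1.2.1 (Primary Analyses) describes a three-period, three-treatment crossover in which 250 mg always precedes 500 mg and placebo may fall in any period. On allocation: "One third of the subjects are randomized to each of these sequences". The model has two three-level factors, drug condition and period. On testing: "An overall F-test of the condition effect will test for differences in response across the three drug doses", followed by contrasts. On variances: "Mixed effects models can allow for different error variances for different sessions". On the covariance model: "a relatively simple covariance structure model (e.g. heterogeneous compound symmetry model) should be sufficient to account for within-subject correlations".

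These sentences stand in the paragraph on adverse events. The next paragraph extends the approach to systolic and diastolic pressure, heart rate and QTc, which are "expressed as AUC, 2-minute values and maximal values) will be similarly analyzed". Section 5.1.1 lists these cardiovascular responses among the primary outcome measures. The synopsis gives the sample size as "12 completers, 21 estimated to enroll".

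The documents state no significance level, df method, small-sample correction, fallback covariance structure, standard deviations or within-subject correlation.

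**The concern.** Heterogeneous compound symmetry is not a small model for this trial. It has four covariance parameters (three session variances and one correlation), to be estimated from 12 subjects with three sessions each. The estimated variances weight the observations when condition effects are estimated, and an uncorrected F- or t-test then treats them as known. With so few subjects the standard errors come out too small.

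At stake is the calibration of the tests on primary safety measures. A CLAV–cocaine interaction on BP, HR or QTc could be declared too often when none exists. Any interval reported would be too narrow, which also makes it easier to appear to exclude a rise that is real. Section 5.2.1 says that these safety data are needed before an outpatient efficacy study.

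**Working it through.** The plan gives no error rate to reproduce, so the check is a simulation of its own design under no drug effect.

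**Inputs from the documents:** 12 completers, three sequences with equal allocation (4 per sequence), three sessions each, fixed effects for condition and period, overall test of condition with 2 numerator df, variances differing by session.

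**Assumptions, because the documents give no figure:** 5% level (two-sided for contrasts), normal data, within-subject correlation 0.2, 0.5 or 0.8, session SDs equal or in the ratio 1:1.5:2.

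**Model.** For subject *i* in session *j*: Var(y_ij) = σ_j², Cov(y_ij, y_ik) = ρσ_jσ_k. This is fitted by REML. The uncorrected statistic is F = (Lb)ᵀ[L(XᵀV̂⁻¹X)⁻¹Lᵀ]⁻¹(Lb)/2, with V̂ treated as known.

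**Degrees of freedom.** There are 12 × 3 = 36 observations and 1 + 2 + 2 = 5 mean parameters.
- Residual: 36 − 5 = 31.
- Within-subject: 36 − 1 − 11 − 2 − 2 = 20.

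**False-positive rate of the overall F-test**, 6,000 data sets per row (Monte Carlo SE √(0.095 × 0.905/6000) ≈ 0.4 points). HCS is heterogeneous compound symmetry with session variances.

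| Correlation, SDs | Plain CS, F(2,20) | HCS, 20 df | HCS, 31 df | HCS, Satterthwaite df | HCS, Kenward-Roger |
|---|---|---|---|---|---|
| 0.2, equal | 4.9% | 9.6% | 10.7% | 8.9% | 5.6% |
| 0.5, equal | 5.1% | 9.5% | 10.6% | 9.1% | 5.6% |
| 0.8, equal | 5.1% | 9.1% | 10.2% | 8.9% | 5.2% |
| 0.5, 1:1.5:2 | 4.5% | 9.3% | 10.5% | 8.8% | 5.3% |

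The plain compound symmetry column calibrates the simulation: with equal variances it should give 5%, and it does. Satterthwaite df do not cure the problem, because they change the reference distribution but leave the standard errors too small. Kenward-Roger corrects both.

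**Contrasts with placebo.** The unadjusted t on 20 df rejects in 7.7–8.1%, so a nominal 95% interval covers 100 − 8.1 = 91.9% to 100 − 7.7 = 92.3%. With Kenward-Roger the contrasts reject in 5.1–5.5%.

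**Spread between simulations.** Smaller simulations of the same design, with more Monte Carlo error, gave 9.0–10.8% on 20 df, up to 11.7% on 31 df, and 7.2–9.5% for contrasts. Hence the rounded ranges: about 9–10%, 10–12% and 7–10%.

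**Sensitivity to what the plan leaves open**
- Variances indexed by drug condition: 6.2% on 20 df, 6.9–7.1% on 31 df.
- All 21 expected enrollees with complete data: df = 63 − 1 − 20 − 2 − 2 = 38, rate 7.3%.
- 12 completers plus 9 subjects with partial data, under an assumed dropout pattern: 8.4% (872 data sets, Monte Carlo SE about 0.9 points).

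**The case against.** A reader might infer that the plan commits to an uncorrected test and will therefore double the false-positive rate of the cardiovascular analyses. The documents do not support that. Heterogeneous compound symmetry is offered as an example, unequal session variances are something the model may allow, and no df method is fixed. Plain compound symmetry, or heterogeneous compound symmetry with Kenward-Roger, would both be consistent with the text. Choosing between the plain and heterogeneous structures by AIC gave 7.1% in simulation. This objection stands and makes the point conditional. It does not remove the point: the structure is the only one named, it is called sufficient, and nothing tells the analyst to adjust.

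A second tempting reading is that the near-doubling applies to contrasts and intervals as well. It belongs to the 2-df overall test. In the largest simulation, contrasts were inflated about 1.6-fold (8.1/5 ≈ 1.6), and the documents plan no intervals for these measures.

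Third, the practical consequence is limited. This is a Phase 1b study with no stated p-value decision rule; eligibility for the 750 mg day rests on laboratory results, vital signs and adverse events; and full listings are promised. Extra false signals are arguably the less harmful error in a safety study. Multiplicity also matters: four parameters in three forms make 4 × 3 = 12 overall tests. With no drug effect, the expected number of false positives is 12 × 0.05 = 0.6 at the nominal rate and 12 × 0.09 to 12 × 0.10, about 1.1 to 1.2, at the inflated rate. All of this bears on severity. None of it is a reason to leave the tests miscalibrated when the correction is nearly free.

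Finally, the covariance sentence stands in the adverse-event paragraph and reaches BP, HR and QTc only by the statement that they are handled similarly. That is the natural reading, but it is an inference.

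**Conclusion.** The concern holds in conditional form. It rests on session-specific heterogeneous compound symmetry being fitted in 12 completers without a small-sample correction, and on the assumed 5% level and normal data. The result hardly moved across the correlations and SD ratios tried, and neither choosing 31 df nor Satterthwaite df avoids it. The SAP's reference to sessions favours indexing the variances by session, which is the less favourable case; the condition-indexed and 21-subject cases show milder inflation. The finding covers only the continuous cardiovascular summaries. It says nothing about the binary adverse-event model, which was not simulated. Label: cheap improvement.

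**What to change.** In 5.2.1.2.1, for the continuous crossover outcomes, state the significance level and add one of the following.

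- Whenever heterogeneous compound symmetry is fitted, use the Kenward-Roger adjustment (standard errors and df) for the overall F-test, the contrasts and any intervals.
- Or make plain compound symmetry (random subject intercept), with F on 2 and 20 df for 12 completers, the primary model, and fit heterogeneous compound symmetry with Kenward-Roger as a sensitivity analysis.

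The first keeps the structure the SAP already favours. The second is simpler; its overall test stayed at 4.5% with session SDs of 1:1.5:2, but its pairwise contrasts under unequal variances were not checked here. The sentence should also say whether variances are indexed by session or by condition, and whether subjects with partial data enter the model.

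The cost is one sentence and one software option, with slightly wider intervals and slightly less sensitivity to real effects. No additional subjects or measurements are needed.

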1. PK of cocaine alone will be compared statistically with PK when both Cocaine and CLAV (250 mg, 500 mg) are present. Both the PK of cocaine and its major metabolite,

BE, will be evaluated with both doses of CLAV. PK will be sampled close to T_{max} and drug levels during combination therapy will be compared with drug levels during treatment with each drug alone.

- PK of CLAV alone will be compared statistically at both doses of CLAV (250 mg, 500 mg) PK will be sampled close to T_{max}. If possible, important gender differences in CLAV PK will be explored.
- 3. *PD. Pupil diameter* (over time) after Cocaine infusion alone (with PBO) will be compared with pupil diameter (over time) after Cocaine infusion with CLAV at both doses (250 mg, 500 mg).

Exploratory:

- Subjective effects of cocaine alone (PBO) will be compared with subjective effects of cocaine and CLAV (250 mg, 500 mg, 750 mg) using both the Visual Analog Questionnaire (VAQ) and the Visual Analog Scales (VAS) for each condition (COC+PBO vs. COC+CLAV). The perceived value of cocaine alone (PBO) will be compared with the perceived value of cocaine in combination with CLAV (250 mg, 500 mg, 750 mg) using the Drug Value Questionnaire (DVQ) for each condition (COC+PBO vs. COC+CLAV). Cocaine craving associated with cocaine alone (PBO) will be compared with the craving associated with cocaine alone (PBO) will be compared with the craving associated with cocaine alone (PBO) will be compared with the craving associated with cocaine alone (PBO) will be compared with the craving associated with cocaine alone (PBO) will be compared with the craving associated with cocaine alone (PBO) will be compared with the craving associated with cocaine alone (PBO) will be compared with the craving associated with cocaine alone (PBO) will be compared with the craving associated with cocaine alone (PBO) mg, 750 mg) using measured by Cocaine Craving Questionnaire-Brief (CCQ-Brief).
- 2. *The subjective effects of clavulanic acid without cocaine* (250 mg, 500 mg, and 750 mg) on mood and personality will be assessed using the Profile of Mood States (POMS) score for each dose of CLAV compared with the score on PBO. The effects of CLAV on the abuse liability using the Addiction Research Center Inventory (ARCI) will be compared at each dose of CLAV (250 mg, 500 mg, and 750 mg) compared with PBO score.

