5.2 Data Analysis Plan

5.2.1 Primary Outcome Measures

The primary objective of this study is to assess the safety and tolerability of CLAV in combination with cocaine to generate data regarding the safety of the combination of CLAV and cocaine in relevant doses of both drugs. This is required prior to an outpatient efficacy study of CLAV for cocaine use disorders. Secondary objectives are to assess whether cocaine alters serum levels of CLAV and to assess serum levels of CLAV at both doses of CLAV in study subjects. Exploratory objectives are to assess the subjective ratings of drug effects with regard to craving and mood. Summary statistics will be provided for all safety, tolerability and subjective data. In addition to the analyses specified below, listings of all data for each patient will be provided.

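### Subjective-effect scores are only to be listed and summarised by dose, without the period adjustment the primary model has, so any drift over study days enters the dose-versus-placebo differences

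*Combined protocol and SAP*

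**What the plan says.** Section 4 (Abstract), exploratory endpoint 1, frames the subjective measures as comparisons. For VAQ and VAS: "Subjective effects of cocaine alone (PBO) will be compared with subjective effects of cocaine and CLAV (250 mg, 500 mg, 750 mg". For DVQ: "The perceived value of cocaine alone (PBO) will be compared with the perceived value of cocaine in combination with CLAV". For CCQ-Brief: "Cocaine craving associated with cocaine alone (PBO) will be compared with the craving", where the rest of the sentence is garbled in the extracted text. Exploratory endpoint 2 likewise sets POMS and ARCI at each CLAV dose against the placebo score.

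The analysis text is thinner. Section 5.2.1.2.3 covers "Subjective effects of cocaine, as measured by check lists, visual analog and rating scales", which "will be listed for each patient and summarized for each group". Section 5.2.1 adds: "Summary statistics will be provided for all safety, tolerability and subjective data". Section 5.2.3 labels the data exploratory with regard to efficacy. None of these gives a contrast, an interval or a period term.

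Section 5.2.1.2.1 does give a suitable structure for the primary analyses: a mixed model with a three-level condition factor and a three-level period factor. The sequences, allocated one third each, are "PBO, Low (250 mg), Medium (500 mg)}, {Low, PBO, Medium}, and {Low, Medium, PBO". The same approach is then carried over by explicit cross-reference to blood pressure, heart rate and QTc, to adverse events at 750 mg, and to adverse events in the buprenorphine subset. The sentence on subjective effects has no such cross-reference, although it stands in the same paragraph as the last two.

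**The concern.** Dose and study day are not balanced. The ascending-dose rule puts 250 mg early in the stay and 500 mg late, and 750 mg is on Day 5 for everyone. Liking, perceived value and craving are self-ratings that could plausibly change with repeated daily 40 mg infusions and with days in hospital. If they do, a summary by dose carries that change into the difference from placebo, with opposite signs for 250 and 500 mg. The pattern can resemble a dose-response when there is none.

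The sponsor already includes period in the primary model, yet the plan does not use it for scales that may be at least as open to day effects. What is at stake is the reading of the dose-specific subjective results.

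**Working it through.** The plan gives no effect size, SD, power or day effect for these scales, so there is no figure of its own to reproduce. The check uses the three arms in the Abstract (Treatments), equal allocation, and 12 completers (4 per arm).

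**1. Mean study day by condition.**

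| Condition | Days in Arms 1, 2, 3 | Mean day |
|---|---|---|
| 250 mg | 2, 2, 3 | 7/3 = 2.33 |
| Placebo | 4, 3, 2 | 9/3 = 3.00 |
| 500 mg | 3, 4, 4 | 11/3 = 3.67 |
| 750 mg | 5, 5, 5 | 15/3 = 5.00 |

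**2. Bias in raw differences, no drug effect, drift of b points per day.** Bias = b × (difference in mean day):
- 250 mg − placebo: (2.33 − 3.00)b = −0.67b
- 500 mg − placebo: (3.67 − 3.00)b = +0.67b
- 500 mg − 250 mg: (3.67 − 2.33)b = +1.33b
- 750 mg − placebo: (5.00 − 3.00)b = +2.00b
- average of 250 and 500 mg − placebo: (2.33 + 3.67)/2 − 3.00 = 0, so no bias

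The last result does not need linearity. With day effects p2, p3 and p4, the 250 mg mean carries (2p2 + p3)/3, the 500 mg mean (p3 + 2p4)/3 and the placebo mean (p2 + p3 + p4)/3. The two doses differ from placebo by (p2 − p4)/3 and (p4 − p2)/3, which cancel on averaging.

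**3. Size under an assumed drift.** The documents do not give b, and it may be zero, in which case there is no bias. If it were 3 to 10 points per day in either direction, the absolute bias would be:
- each Days 2-4 dose versus placebo: 0.67 × 3 = 2 to 0.67 × 10 = 6.7 points
- 500 versus 250 mg: 1.33 × 3 = 4 to 1.33 × 10 = 13.3 points
- 750 mg versus placebo: 2 × 3 = 6 to 2 × 10 = 20 points

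**4. What a period term does.** Arms 2 and 3 swap 250 mg and placebo between Days 2 and 3. Arms 1 and 2 swap 500 mg and placebo between Days 3 and 4. Each dose-versus-placebo contrast can therefore be separated from day. Least squares with subject, condition and period on Days 2-4 gives zero drift bias for all three contrasts. Variances, with σ² the within-subject error variance:

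| Contrast | No period term (22 error df) | With period (20 error df) |
|---|---|---|
| 250 or 500 mg − placebo | 2/12 = 0.167σ² | 0.200σ² |
| 500 − 250 mg | 0.167σ² | 0.300σ² |

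The standard error rises by √(0.200/0.1667) = 1.10 for each dose versus placebo and by √(0.300/0.1667) = 1.34 for 500 versus 250 mg. The second rises more because no arm gives 500 mg before 250 mg.

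**5. 750 mg.** Adding Day 5 with its own period effect gives a design of rank 17 with 18 columns, so 750 mg cannot be separated from Day 5. It can be estimated only under an added assumption such as a linear day trend (variance 0.467σ²).

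**The case against.** The strongest reply is that descriptive reporting is a legitimate choice for exploratory scales in a safety trial with 12 completers. The Abstract calls for a statistical comparison of the PK data but says only that the subjective data will be compared. Side-by-side summaries with individual listings could meet that wording. This stands in part: a reader might infer that a formal test was promised, and the documents do not say so. It does not answer the bias, since a descriptive difference between dose means carries the drift just as a tested one would.

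Other readings go further than the documents allow:
- **That drift would appear as an overall CLAV effect.** It would not. The two Days 2-4 doses shift in opposite directions and their average is unbiased.
- **That the problem is 4 to 13 points.** That figure is for 500 versus 250 mg under an assumed drift. The endpoint defines comparisons with placebo, for which the same assumption gives 2 to 6.7 points on Days 2-4.
- **That summaries by group make no sense in a crossover, or lose the pairing.** The SAP uses group to mean treatment condition. With complete data, differences of dose means equal mean paired differences. What is missing is the period adjustment and a measure of precision.
- **That the results will shape the outpatient efficacy study.** Section 5.2.1 ties the safety data to that study, not the subjective ratings, and section 5.2.3 limits what they can say on efficacy.

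It is also fair that the drift is assumed. In a simulation of unadjusted paired tests at 5% (3000 runs per setting), drifts of 0.25 and 0.5 within-subject SD per day raised rejection for each Days 2-4 dose versus placebo only to about 6% and 8%. The plan proposes no such test.

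**Conclusion.** The concern holds in a limited form. The Abstract sets up comparisons with placebo, and the SAP plans only listings and summaries that leave study day mixed with dose. The imbalance follows directly from the sequences: −0.67b, +0.67b and +2.00b for 250, 500 and 750 mg versus placebo. The size of b is unknown.

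The calculation rests on equal numbers of completers per sequence, complete data, a day effect common to all subjects, and no carryover. Unequal loss from the sequences would change the mean days; the documents give no basis for sizing that. The period model corrects the two Days 2-4 doses but cannot rescue 750 mg. This should be put right, but it does not touch the primary safety analysis.

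**What to change.** In section 5.2.1.2.3, keep the listings and summaries and add, for VAQ, VAS, DVQ and CCQ-Brief, exploratory estimates of 250 mg and 500 mg versus placebo with 95% intervals. Obtain them from a continuous-response version of the section 5.2.1.2.1 model: condition and period fixed, subject random, Days 2-4. A continuous version is needed because that section describes the model for binary responses. Do the same for POMS and ARCI, which the Abstract also compares with placebo and for which no model is stated. Name the score and time point used from each instrument, and say that the intervals are not adjusted for multiplicity.

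Report 750 mg versus placebo descriptively and apart from these estimates, stating that it is fully confounded with Day 5 and single-blind.

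Rewording the endpoint as purely descriptive would remove the mismatch but leave the day effect in the summaries, so it is the weaker option.

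The cost is SAP wording, a few model runs on data already collected, and intervals about 10% wider for each dose versus placebo. With 12 completers they will be wide in any case, which is acceptable for exploratory endpoints.
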